17.4 Secondary endpoints

17.4.1.1 **Efficacy endpoints**

Classification of re-bleeds will be done by Novo Nordisk as part of the statistical analysis based on bleeding information: A re-bleed is defined as a bleed (worsening of bleeding site conditions e.g. swelling, pain) within 72 hours after stopping treatment of a previous bleed at the same (or subset of the same) anatomical location. If a bleed occurs in the same location 72 hours after stopping, the treatment is defined as a new bleeding episode. Relevant data listings will be repeated for re-bleeds separately. Minor surgery periods will be excluded from the prophylaxis treatment period. Data related to bleeds during these periods will be listed separately.

Successful haemostatic effect of turoctocog alfa on treatment of bleeding episodes during the trial.

Haemostatic effect is assessed on a predefined four point scale: Excellent, Good, Moderate and None. Successful haemostatic response is defined by the categories: success (good or excellent) and failure (none, moderate, missing).

The haemostatic effect and successful haemostatic of turoctocog alfa will be summarised by frequency tables containing count and percentages of all bleeds. Summaries will be made separately by severity of haemophilia A assessed at baseline.

The haemostatic effect and successful haemostatic effect of turoctocog alfa will also be summarised by the following subgroups: Cause of bleeding episode (Spontaneous, Traumatic), Site of bleeding (Central nervous system, Haemarthrosis (Joint), Gastrointestinal, Subcutaneous, Muscular or other), and Classification of bleeding (Mild/Moderate or Severe). Details (cause, site, classification and time) about the bleeding episodes will also be summarised and listed.

All bleeding episodes during trial will be listed including pertinent clinical information.

Total annualised consumption of turoctocog alfa measured during the 8 weeks of treatment

Total consumption of turoctocog alfa (IU/kg/year) during the trial (given for either prevention, treatment of bleeding episodes or during surgery) will be summarised for moderate and severe haemophilia A patients and listed by patient.

Additionally, number of turoctocog alfa infusions (injections/bleed) required per bleeding episode during the 8 weeks of treatment will be summarised. The number of infusions of turoctocog alfa required per bleed will be calculated as the number of infusions of turoctocog alfa used in the time period from start of the bleed to stop of the bleed. The number of infusions will be presented using count and percentages of all bleeds. Presentation will be done separately for moderate and severe haemophilia A patients. Further, the turoctocog alfa consumption per bleeding episode during the 8 | Protocol | Trial ID: NN7008-4304 | CONFIDENTIAL | Date: 13 June 2017 | Novo Nordisk | Version: 2.0 | Status: Final | Page: 64 of 81 |

weeks of treatment will be summarised. The consumption of turoctocog alfa (IU/kg BW/bleed) will be calculated as the consumption of turoctocog alfa used from start of the bleed to stop of the bleed. The consumption will be summarised for moderate and severe haemophilia A patients and listed by patient.

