3.1.2 Current standard of care

Among FVIII concentrates used in India in 2014, 98% consumption was plasma derived FVIII (pd-FVIII) and the remaining 2% was recombinant FVIII (rFVIII).⁵ This partly explains the inadequate supply and delay in supply of FVIII as pd-FVIII alone is not able to meet the patients' requirements as elsewhere in the world. Hence a significant proportion of Haemophilia A patients in India are still treated with blood or blood derived products, namely fresh frozen plasma and cryoprecipitate. The prevalence of HIV, Hepatitis B and Hepatitis C burden among patients with haemophilia due to use of blood products is approximately 1 %, 6 % and 30 % respectively. \(\frac{7}{8}\)

Protocol		Date:	13 June 2017	Novo Nordisk
Trial ID: NN7008-4304	CONFIDENTIAL	Version:	2.0	
UTN:U1111-1179-5950	CONFIDENTIAL	Status:	Final	
EudraCT no.:2017-002281-46		Page:	14 of 81	

The risk of infections in patients with Haemophilia A due to prions and small non-enveloped viruses like parvovirus B19 exists as these are neither removed nor inactivated in any of the currently available pd-FVIII in India. 5, 9, 10 The currently available first generation rFVIII uses albumin and other human/animal serum or proteins in various stages of production process which lowers their final purity. 5, 9 Concentrates of lower purity may give rise to allergic reactions. In addition it does not undergo any standard recommended purification technique namely solvent detergent method or nanofiltration as per World Federation of Haemophilia (WFH). Hence availability of recombinant FVIII concentrates is considered as an unmet need for management of patients of Haemophilia A in India.

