6.5 Criteria for premature discontinuation of trial product

A patient must be prematurely discontinued from trial product if the following applies:

- 1. Included in the trial in violation of the inclusion and/or exclusion criteria.
- 2. Simultaneous participation in another clinical trial of an approved or non-approved investigational medicinal product.
- 3. High titer FVIII inhibitor (>5 BU), confirmed by central laboratory.
- 4. Planned or emergency major surgery.
- 5. Severe allergic or anaphylactic reaction to trial product.
- 6. Clinically relevant thromboembolic event which requires treatment with anticoagulants.
- 7. Lack of haemostatic effect of the trial product.
- 8. Use of other FVIII products
- 9. Use of FVIII containing products (blood components, PCC) for more than 5 EDs.

The subject may be prematurely discontinued from trial product at the discretion of the investigator due to a safety concern.

See section 8.1 for procedures to be performed for subjects discontinuing trial product prematurely.

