8.3.1 Bleeding episodes

During the entire trial period all bleeding episodes must be entered in the diary, see section 8.6.2.

The following will be recorded in the diary for bleeding episodes:

- Bleeding episode start date and time
- Bleeding episode stop date and time, see Table 8–2
- Bleeding episode location (joint, muscle, skin, stomach (gastrointestinal bleeding episode), mucosal (mouth, gums, nose), urinary system, central nervous system, other)
 - If joint is chosen, specify location: knee, ankle, wrist, fingers, elbow, shoulder, hip, toes, jaw
 - If muscle or skin is chosen, specify location: arm, leg, hand, buttocks, head/neck, chest, back, stomach, foot
- Cause of bleeding episode (spontaneous, traumatic, surgical bleeding episode) see Table 8–5
- Other non-medical therapy used
- Evaluation of the achieved haemostatic response (Excellent, Good, Moderate or None), see Table 8–3
- Severity (mild/moderate or severe) evaluated by investigator, see Table 8–4

Table 8–2 Definition of stop of a bleeding episode

Stop time is:

When the patient/parent or LAR experiences/observes signs of cessation of the active bleeding episode such as; pain relief, no increase in swelling/limitation of motion and improvement in other objective signs of the bleeding episode **Stop time is not:**

When pain and objective signs of the bleeding episode are completely resolved

Table 8–3 Definition of haemostatic response

Category	Definition
Excellent	abrupt pain relief and/or unequivocal improvement in objective signs of bleeding episode within approximately 8 hours after a single injection
Good	definite pain relief and/or improvement in signs of bleeding episode within approximately 8 hours after an injection, but possibly requiring more than one injection for complete

Protocol		Date:	13 June 2017	Novo Nordisk
Trial ID: NN7008-4304	CONFIDENTIAL	Version:	2.0	
UTN:U1111-1179-5950	CONFIDENTIAL	Status:	Final	

Page:

32 of 81

Category	Definition
	resolution
Moderate	probable or slight beneficial effect within approximately 8 hours after the first injection; usually requiring more than one injection
None	no improvement, or worsening of symptoms within approximately 8 hours after the first injection; usually requiring more than one injection

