The patient or parent/LAR must in the diary assess the haemostatic efficacy for treatment of bleeding episodes, but the investigator must together with the patient during the diary review evaluate the correctness of the evaluation.

Table 8–4 Definition of bleeding episode severity

EudraCT no.:2017-002281-46

Category	Definition	Comment
Mild/Moderate	Minor bleeding episodes which are uncomplicated joint bleeding episodes, muscular bleeding episodes without compartment syndrome, mucosal or subcutaneous bleeding episodes	
Severe	Major bleeds that require hospitalisation; intracranial, retroperitoneal, iliopsoas and internal neck bleeds; muscle bleeding episodes with compartment syndrome; bleeding episodes associated with a significant decrease in the haemoglobin level (>3g/dl). Traumatic bleeding episodes at other locations than described above can always be considered severe at the investigators discretion.	These bleeding episodes must be treated immediately at home or at the local emergency room, and the trial site must be contacted

Table 8–5 Definition of bleeding episode categorisation

Category	Comment
Spontaneous	Not linked to a specific event
Traumatic	Caused by a specific, known action or event (e.g. injury or exercise)
Surgical	Bleeding episodes during surgery

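### A bleed in which another FVIII-containing product was used early can count as a turoctocog alfa success, because 17.4.1.1 scores on the rating alone

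*Combined protocol and SAP*

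**What the plan says.** **Scoring.** Protocol section 17.4.1.1 defines the endpoint by the rating: "Successful haemostatic response is defined by the categories: success (good or excellent) and failure (none, moderate, missing"). The results "will be summarised by frequency tables containing count and percentages of all bleeds", and are repeated by cause, site and severity of the bleed. No condition refers to other products.

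**Rating.** Table 8-3 (section 8.3.1) ties each category to the response within about 8 hours of an injection. It does not name the product injected.

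**Tolerated use.** Section 6.5 lists among the discontinuation criteria "Use of other FVIII products" (criterion 8, no threshold), "Use of FVIII containing products (blood components, PCC) for more than 5 EDs" (criterion 9) and "Lack of haemostatic effect of the trial product" (criterion 7).

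**Data capture.** The bleed record has a field for "Other non-medical therapy used". Other medication is recorded as concomitant medication with indication and start and stop dates (section 8.2.3), and section 8.6.2 requires every treatment to be entered in the diary.

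**Consumption per bleed.** The summaries of injections and IU/kg per bleed in section 17.4.1.1 count turoctocog alfa only, from bleed start to bleed stop.

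**The concern.** The endpoint is labelled as the haemostatic effect of turoctocog alfa. If a bleed was controlled partly or wholly by another source of FVIII, its rating describes the combined treatment. The plan foresees such use, since criterion 9 tolerates it up to a limit, but gives no rule for scoring the bleed.

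The setting makes the event conceivable. Section 3.1.2 says that "a significant proportion of Haemophilia A patients in India are still treated with blood or blood derived products", and Table 8-4 says of severe bleeds: "These bleeding episodes must be treated immediately at home or at the local emergency room, and the trial site must be contacted".

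At stake is the success percentage and its breakdown by bleed severity. The per-bleed figures would be affected too: a bleed supplemented with another product would look both successful and economical, because only its turoctocog alfa part is counted.

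**Working it through.** **1. Is the use compatible with staying in the trial?** Criterion 9 applies above 5 exposure days, so days 1 to 5 do not trigger it. Section 5.1 plans at least 20 exposure days over 8 weeks; 5/20 = 25% of that minimum.

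**2. How would such a bleed be scored?** Reading Table 8-3 together with 17.4.1.1:

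| When the other FVIII-containing product is given | Result under the plan |
|---|---|
| After turoctocog alfa has shown little or no effect at about 8 hours | Rating Moderate or None: failure |
| Before, with or instead of turoctocog alfa, bleed then rated Good or Excellent | Success |
| After turoctocog alfa but inside the 8-hour window, bleed then rated Good or Excellent | Success |
| Any time, rating missing | Failure |

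The gap is rows two and three.

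**3. Does another rule remove these bleeds?** No. Section 17.2 reserves exclusion of data points for exceptional cases, documented before database lock. Section 18.5 keeps data already collected from patients who withdraw. The investigator checks the rating with the patient (section 8.3.1), but has no criterion for attributing the response to one product.

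**4. Can the bleeds be identified?** Yes, from concomitant medication dates (8.2.3) and diary treatment records (8.6.2). Section 8.2.3 asks for dates, not times, whereas bleed start and stop carry times (8.3.1). Same-day use therefore needs a convention.

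**5. Size (illustration only).** The plan gives no precision or power figure for this endpoint and no frequency of such use. Inputs: 60 patients planned to start (6.1), 8 weeks of treatment, and mean annualised bleeding rates of 6.5 in the earlier adult and adolescent trial and 2.4 in its extension (3.1.3).

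- Expected bleeds = patients × annual rate × 8/52.
- At 6.5 per year: 60 × 6.5 × 8/52 = 60 bleeds; one bleed = 1/60 = 1.7 points.
- At 2.4 per year: 60 × 2.4 × 8/52 = 22 bleeds; one bleed = 1/22 = 4.5 points.

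Now assume 60 bleeds and, from the 81% in the earlier adult and adolescent trial, 0.81 × 60 = 48.6, rounded to 49 successes (81.7%). Let k be the number of those successes in which another FVIII-containing product was used:

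| k (assumed) | Rating as recorded, 49/60 | Scored as failures, (49 − k)/60 | Excluded, (49 − k)/(60 − k) |
|---|---|---|---|
| 0 | 81.7% | 81.7% | 81.7% |
| 1 | 81.7% | 80.0% | 81.4% |
| 3 | 81.7% | 76.7% | 80.7% |
| 6 | 81.7% | 71.7% | 79.6% |
| 12 | 81.7% | 61.7% | 77.1% |

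In a subgroup of n bleeds, such as severe bleeds, one bleed moves the rate by 100/n points.

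**The case against.** A reader might infer that a bleed which turoctocog alfa failed to control, and which was then rescued with plasma or cryoprecipitate, is scored as a success. The documents do not support that. Table 8-3 fixes the rating at about 8 hours, so non-response by then is Moderate or None whatever follows. If the bleed had clearly improved by then, Good is a fair rating of turoctocog alfa even if something else was given later. Section 5.3 also has bleeds treated with turoctocog alfa injections, so the unnamed injection in Table 8-3 is most naturally read as trial product. This stands, and confines the problem to early, concurrent or substitute use.

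A reader might also infer that the data are not collected because the bleed record mentions only non-medical therapy. That is not so: sections 8.2.3 and 8.6.2 capture other treatments, so no diary change is needed.

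Nothing shows that such bleeds will occur. Section 3.1.2 describes national practice under short supply, whereas trial patients hold product at home with bleed doses set in advance. The 6.5 rate comes from patients with severe disease, while this trial also enrols moderate disease. Criteria 7 and 8 remove some of the relevant patients from treatment, with the reason recorded. All of this stands as to frequency. It does not supply a scoring rule for the bleed itself.

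Lastly, the endpoint is secondary and descriptive, with no formal testing, and scoring every affected bleed as a failure can be too harsh. That limits the weight of the point and is why sensitivity analyses are needed.

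**Conclusion.** The point holds as a gap in the scoring rule. Sections 6.5 and 17.4.1.1 together let a bleed in which another FVIII-containing product was given before, with or instead of turoctocog alfa, or within about 8 hours of it, count as a turoctocog alfa success. The per-bleed injection and IU/kg summaries then show only part of the treatment. Compared with scoring these bleeds as failures, the effect can only be upward.

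The size per bleed is about 1.7 points with 60 bleeds and 4.5 points with 22. Those totals assume that 60 patients are each observed for 8 weeks and bleed at the rates of the earlier trials. The number of affected bleeds is unknown and may be zero, so the documents do not support a claim that the reported rate will be materially inflated. The rule is worth stating because it is cheap, and because a scoring choice made after the bleeds have been seen would be open to challenge. No conclusion about the primary inhibitor endpoint depends on it.

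**What to change.** In section 17.4.1.1, or in the SAP that section 17 allows for, before database lock:

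- Score as failure any bleed for which another FVIII-containing product (concentrate, blood component or PCC) was given between bleed start and stop. Identify these from concomitant medication dates and diary treatment records, counting same-day use as within the bleed. Keep the rule to FVIII-containing products; a wider class of haemostatic products is undefined here and could take in routine adjuncts.
- Add two sensitivity analyses: one with the rating as recorded, one excluding these bleeds.
- Flag the bleeds in the listings and in the per-bleed injection and consumption summaries.

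Separately, the sponsor should reconcile criteria 8 and 9 of section 6.5, since one has no threshold and the other applies only above 5 exposure days. Which reading is right is for the sponsor to settle. Nothing here changes what patients may receive.

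The cost is a short scoring paragraph, two extra analyses and a flag. The reported success rate may be slightly lower, and a bleed that had already responded to turoctocog alfa before the other product was given may be scored conservatively. The recorded-rating analysis shows how much that matters.

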17.4.1.2 Safety endpoints

• Frequency of ARs and SARs reported until follow-up, 12 weeks after the first treatment.

An AR is an AE where the causality is rated as probable or possible by the investigator, similar for SAR. ARs and SARs will be analysed by severity of haemophilia A assessed at baseline.

All ARs and SARs will be summarised by frequency of events and frequency of patients with any event. Similar summaries cross-classified by severity will be made.

All AE's and SAEs will be summarised by frequency of events and frequency of patients with an y event. Similar summaries cross-classified by severity will be made. These summary will be made by severity of haemophilia A assessed at baseline.

ARs, SARs, AEs, SAEs will be summarised by SOC and PT.

Furthermore, listings will be provided displaying all AEs and SAEs including pertinent clinical information

Separate list will be performed for adverse events with onset before first trial drug or after the follow up visit (if any).

• Frequency of allergic or infusion reactions related to the trial product reported until follow-up,12 weeks after first treatment.

This endpoint will be reported without additional summaries or listings. The reporting will be based on the overall summaries and listings for ARs and SARs.

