Criteria for premature discontinuation of trial product			X	X			X
Concomitant illness		X					
Concomitant medication		X	X	X	X		X
Haemophilia treatment and bleed history		X					
Medical history		X					
Details of Haemophilia		X					
Informed consent	X	X					
Informed assent	X^{b}	X^{b}					
Genotyping consent, optional		X ^c					
Biospecimen consent		X^{b}					
Demography		X					
Body measurements		X					
Height		X					
Body weight		X	X	X			Xb
EFFICACY							
Bleeding episodes			X^d	X ^d	X ^d		

Protocol Trial ID: NN7008-4304 UTN:U1111-1179-5950 EudraCT no.:2017-002281-46

CONFIDENTIAL

Date: Version: Status: Page:

3 June 2017 2.0 Final 11 of 81

13 June 2017 | Novo Nordisk

						1
Information visit	Screening	Baseline	Treatment	End of trial	Follow-up	Unscheduled Visit
0		_	2	4	-	
			_		_	
0	±2	±7	±3	±3	±3	
	X				X	X
		X	X			X
	X					
		Xe	Xe			Xe
		Xe	Xe			Xe
		Xf	Xf	Xf		X^{f}
	X			X		
	X^{g}					
	X			X		
	X^h					
	X^h					
	X ^c					
	Xi			Xi		X ^b
		X^{j}				X^{j}
		X	X			
	X	X	X	X		X ^b
		X	X	X		
			X	X		
		X	X^{b}			X ^b
	X					
		X	X	X		
	Information visit	0 1 -4 -3 0 ±2 X X X X X X X X X X X X X	0	0	0	0 1 2 3 4 5 -4 -3 0 4 8 12 ^a 0 ±2 ±7 ±3 ±3 ±3 X X X X X X X X X X X X X X X X X X X X X X X X X X X X X X X X X X X X X X X X X X X X X X X X X X X X X X X X X X X X X X X X X X X X X X X X X X X X X X X X X X X X X X X X X X X X X X X X X X X X X X X X X X X X X X X X X X X X X X X X X X X X X X X X X X X X X X X X X X X X X X X X X X X X X X X X X X X X X X X X X X X X X X X X X X X X X X X X X X X X X X X X X X X X X X X X X X X X X X X X X X X X X X X X X X X X X X X X X X X X X X X X X X X X X X X X X

Protocol		Date:	13 June 2017	Novo Nordisk
Trial ID: NN7008-4304	CONFIDENTIAL	Version:	2.0	
UTN:U1111-1179-5950	CONFIDENTIAL	Status:	Final	
EudraCT no.:2017-002281-46		Page:	12 of 81	

- X^a If patient has withdrawn the follow-up-visit must be performed 4 weeks after end of trial visit
- X^b If applicable
- X° Genotype consent is not mandatory at visit 1, but has to be collected before genotype is sampled, see section 8.5.3.1
- X^d Bleeding episodes and dosing information are recorded in the diary
- X^e If hypersensitivity reaction or technical complaints are identified, please ensure to complete the relevant form, see sections 12.1.5 and 12.1.6
- X^f If patient had any surgical interventions (minor surgery), please ensure to complete the surgery form, see section 8.4.5

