4.2.2 Secondary endpoints

- Frequency of adverse drug reactions (AR) and serious adverse reactions (SAR) reported until follow-up, 12 weeks after first treatment
- Successful haemostatic effect of turoctocog alfa in the treatment of bleeding episodes during 8 weeks of treatment
- Total annualised consumption of turoctocog alfa measured during the 8 weeks of treatment
- Frequency of allergic or infusion reactions related to the trial product reported until follow-up, 12 weeks after first treatment

 Protocol
 Date:
 13 June 2017
 Novo Nordisk

 Trial ID: NN7008-4304
 Version:
 2.0
 2.0

 UTN:U1111-1179-5950
 Status:
 Final

Page:

17 of 81

5 Trial design

EudraCT no.:2017-002281-46

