12.1.5 Adverse events requiring additional data collection

AEs requiring additional data collection are AEs where the additional data will benefit the evaluation of the safety of the trial product.

In this trial the following AE require the completion of specific event forms in the eCRF

• Hypersensitivity reaction including anaphylactic reactions

Clinical criteria for diagnosing anaphylaxis (Sampson et al. $\frac{30}{2}$).

Anaphylaxis is highly likely when any one of the following three criteria is fulfilled:

- Acute onset of an illness (minutes to several hours) with involvement of the skin, mucosal tissue, or both (e.g. generalised hives, pruritus or flushing, swollen lips-tongue-uvula) AND AT LEAST ONE OF THE FOLLOWING:
 - Respiratory compromise (e.g. dyspnea, wheeze-bronchospasm, stridor, reduced peak expiratory flow [PEF], hypoxemia)
 - Reduced BP or associated symptoms of end-organ dysfunction (e.g. hypotonia [collapse], syncope, incontinence)
- 2. Two or more of the following that occur rapidly after exposure to a likely allergen for that patient (minutes to several hours):

Protocol		Date:	13 June 2017	Novo Nordisk
Trial ID: NN7008-4304	CONFIDENTIAL	Version:	2.0	
UTN:U1111-1179-5950	CONFIDENTIAL	Status:	Final	
EudraCT no.:2017-002281-46		Page:	51 of 81	

- o Involvement of the skin-mucosal tissue (e.g. generalised hives, itch-flush, swollen lips-tongue-uvula)
- Respiratory compromise (e.g. dyspnea, wheeze-bronchospasm, stridor, reduced PEF, hypoxemia)
- Reduced BP or associated symptoms (e.g. hypotonia [collapse], syncope, incontinence)
- o Persistent gastrointestinal symptoms (e.g. crampy abdominal pain, vomiting)
- 3. Reduced BP after exposure to known allergen for that patient (minutes to several hours):
 - Systolic blood pressure of less than 90 mm Hg or greater than 30% decrease from that person's baseline

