12.2 Reporting of adverse events

All events meeting the definition of an AE, SAE and AEs leading to discontinuation of trial product must be collected and reported. This includes events from the first trial-related activity after the patient has signed the informed consent until the end of the post-treatment follow-up period. The events must be recorded in the applicable eCRF forms in a timely manner, see timelines below and Figure 12–1.

During each contact with the trial site staff, the patient must be asked about AEs and technical complaints, for example by asking: "Have you experienced any problems since the last contact?"

All AEs, observed by the investigator or patient, must be reported by the investigator and evaluated.

All AEs must be recorded by the investigator on an AE form. The investigator must report the diagnosis, if available. If no diagnosis is available, the investigator must record each sign and symptom as individual AEs using separate AE forms.

For SAEs, a safety information form must be completed in addition to the AE form. If several symptoms or diagnoses occur as part of the same clinical picture, one safety information form can be used to describe all the SAEs.

Protocol	1	Date:	13 June 2017	Novo Nordisk
Trial ID: NN7008-4304	CONFIDENTIAL	Version:	2.0	
UTN:U1111-1179-5950	CONFIDENTIAL	Status:	Final	
EudraCT no.:2017-002281-46		Page:	52 of 81	

For all non-serious AEs, the applicable forms must be signed when the event is resolved or at the end of the trial at the latest.

Timelines for initial reporting of AEs:

The investigator must complete the following forms in the eCRF within the specified timelines:

[figure not shown]
• **SAEs:** The AE form **within 24 hours** and the safety information form **within 5 calendar** days of the investigator's first knowledge of the SAE

Both forms must be signed within 7 calendar days from the date the information was entered in the eCRF.

For AEs/SAEs requiring reporting on a specific event form: In addition to the above the specific event form within 14 calendar days from the investigator's first knowledge of the AE.

If the eCRF is unavailable, the concerned AE information must be reported on a paper AE form and sent to Novo Nordisk by fax, e-mail or courier within the same timelines as stated above. When the eCRF becomes available again, the investigator must enter the information on the form into the eCRF.

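### The secondary endpoint on allergic or infusion reactions has no patient count of its own and no rule for which reactions qualify

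*Combined protocol and SAP*

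**What the plan says.** Section 4.2.2 lists as a secondary endpoint: "Frequency of allergic or infusion reactions related to the trial product reported until follow-up, 12 weeks after first treatment". The summary (section 1) and section 17.4.1.2 repeat it.

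Section 17.4.1.2 then sets the method: "This endpoint will be reported without additional summaries or listings". The next sentence adds: "The reporting will be based on the overall summaries and listings for ARs and SARs".

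The same section describes the outputs relied on. "All ARs and SARs will be summarised by frequency of events and frequency of patients with any event", with a cross-classification by event severity and a presentation by baseline haemophilia severity. In addition, "ARs, SARs, AEs, SAEs will be summarised by SOC and PT". Listings of all AEs and SAEs are also planned. An AR is an AE whose causality the investigator rates probable or possible.

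Data collection goes further than the analysis does. Section 12.1.5 requires a specific event form for: "Hypersensitivity reaction including anaphylactic reactions". The flow chart footnote in section 2 repeats this: "If hypersensitivity reaction or technical complaints are identified, please ensure to complete the relevant form". Section 12.2 sets the deadline: "In addition to the above the specific event form within 14 calendar days" of the investigator's first knowledge. Section 17 does not mention this form.

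**The concern.** A frequency endpoint needs a numerator. Here the plan rules out a dedicated output and points to tables that were not built to supply one. Two gaps follow.

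- **Counting patients.** Events can be added across preferred-term rows, but patients cannot, because one patient may appear in several rows. Section 12.2 makes this realistic: where there is no diagnosis, each sign or symptom is recorded as a separate AE.
- **Deciding what counts.** The term infusion reaction appears only in the endpoint wording. Section 12.5 gives example signs of hypersensitivity and section 12.1.5 gives criteria for anaphylaxis. Neither says which ARs are infusion reactions.

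The trial is open-label, and under section 13.2 eCRF data are available to the sponsor once entered. A choice of qualifying terms made at reporting would therefore be made with the events in view. The primary objective is safety, and section 18.1 names allergic reaction as one of the risks common to recombinant FVIII products.

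**Working it through.** **1. The plan's own figure.** The plan gives no expected rate or precision for this endpoint. The nearest figure is in section 17.1: about 95% probability of seeing at least one affected patient among 50 at 6% incidence, said to hold for other types of adverse event. It reproduces: 1 − 0.94^50 = 0.9547. It is a statement about patients, so the matching summary is a count of patients.

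**2. What the planned tables can determine.** Let T be the number of patients with any AR, q the patient counts in the qualifying preferred-term rows, and u the counts in the non-qualifying rows. The number of patients with a qualifying reaction lies between

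- lower bound: the larger of max(q) and T − sum(u);
- upper bound: the smaller of sum(q) and T.

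If there are no unrelated ARs, sum(u) = 0 and both bounds equal T, so the any-AR row gives the exact answer. Ambiguity therefore needs reactions under several terms and unrelated ARs as well.

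**3. A constructed example.** All counts are hypothetical. The denominator is the 60 patients planned to start trial product (section 6.1). Assume that rash, pruritus and fever qualify and a raised ALT does not, and that all events share one AE severity and all patients one haemophilia severity. Assume also that rash and pruritus share a SOC, with fever and ALT in two others.

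| | Patient 1 | Patient 2 | Patient 3 |
|---|---|---|---|
| Dataset A | rash, pruritus, fever | rash | raised ALT |
| Dataset B | rash, pruritus, raised ALT | rash | fever |

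Both datasets give the same tables: 5 ARs; 3 patients with any AR; rash 2, pruritus 1, fever 1, raised ALT 1; SOC patient counts 2, 1 and 1.

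Bounds: lower = max(2, 3 − 1) = 2; upper = min(2 + 1 + 1, 3) = 3. Both ends are reached:

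- A: patients 1 and 2 qualify, 2/60 = 3.3%.
- B: patients 1, 2 and 3 qualify, 3/60 = 5.0%.

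**4. The effect of the missing rule.** Suppose the only candidate event is one headache rated possibly related. Depending on whether it is called an infusion reaction, the result is 0/60 (0%, exact two-sided 95% upper limit 6.0%) or 1/60 (1.7%, upper limit 8.9%). No table or listing settles that choice.

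**The case against.** The strongest reply is that section 17.4.1.2 relies on listings as well as summaries. With about 60 dosed patients, anyone can go through the AE listing and count each patient once. This stands as far as overlap is concerned. A reader might infer that the patients affected cannot be recovered at all, or that the endpoint will be left without any number. The documents support neither reading: they exclude additional outputs but do not say that no figure will be stated. The listings do not, however, say which ARs qualify.

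A reader might also expect wide ambiguity whenever several terms are involved, for example three single-patient rows read as anything from 1 to 3 patients. If those are the only AR rows, the any-AR patient count gives the exact number. The range opens only when unrelated ARs occur too, and in the example above it spans one patient.

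Third, hypersensitivity cases are already flagged on their own form, and a diagnosed reaction is a single AE. That is right, and it means the allergic part is largely identified. What is missing is the link from the form to the endpoint.

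Fourth, section 17 allows an SAP with more technical detail before database lock. It is optional, so it softens the gap without closing it. The absence of a separate SAP from the supplied text is not held against the plan.

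Finally, a reader might think that an infusion reaction must be tied to a fixed number of hours after injection. The documents give no such window, and the point does not depend on one.

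**Conclusion.** The point holds in a limited form. The stated method gives a named secondary endpoint no summary of its own. The tables it relies on do not in general determine the number of patients affected, and no rule says which ARs are infusion reactions. A hand count from the listings is possible, but its definition would be chosen after the events are known.

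The size is modest. In the hypothetical example the tables leave one patient in 60 unresolved (3.3% or 5.0%), and one disputed event moves the result between 0% and 1.7%. These figures show scale only, because the documents give no expected rate. The endpoint is descriptive with no formal testing. Its analysis set, observation period and relatedness rule are already defined, and the primary endpoint and sample size are unaffected. The missing definition alone would be a matter of detail. What makes the change worthwhile is that a distinct-patient count is better than the stated no-summary rule and costs little.

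**What to change.** Replace the no-summary sentence in section 17.4.1.2 with text such as:

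> The number of events, and the number and percentage of patients in the Safety Analysis Set with at least one event (each patient counted once), will be presented from first dose to the follow-up visit. Qualifying events are ARs (possible or probable) that have a hypersensitivity specific event form or are on a list of infusion-reaction terms fixed and dated before the AE data are reviewed. A short listing will be provided.

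Because the sponsor can see eCRF data as they are entered, the list is best dated before dosing starts; waiting until just before database lock would not serve the purpose. No time window is required. If the sponsor wants one, it should set it in advance.

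The cost is one paragraph, one term list, and one small table with a short listing, using the AE and hypersensitivity forms already collected. The downside is that the term list may bring in some non-specific events.
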